7.3.2 Follow-up of AE, SAE, and Other Reportable Safety Event Information

7.3.3 After the initial AE/SAE report, the investigator is required to proactively follow each participant at subsequent visits/contacts. All AEs, SAEs, and other reportable safety events including pregnancy and exposure during breastfeeding, events of clinical interest (ECIs), cancer, and overdose will be followed until resolution, stabilization, until the event is otherwise explained, or the participant is lost to follow-up.. In addition, the investigator will make every attempt to follow all nonserious AEs that occur in allocated or randomized participants for outcome. Reporting to the IRB

Each participating site will report SAEs, ECIs, pregnancies, and unanticipated problems to their IRB per local and institutional guidelines.

7.4 Coordinating Center Reporting Responsibilities

7.4.1 Reporting to the IRB

Unanticipated problems involving risks to subjects or others will be reported **promptly** to the IRB if they are:

- unexpected;
- related or possibly related to participation in the research; and
- suggests that the research places subjects or others at a greater risk of harm than was previously known or recognized.

If the unanticipated problem does not meet all three (3) criteria listed above, the event does not have to be promptly reported to the Indiana University IRB. However, it should be reported at the time of continuing review.

Prompt reporting of unanticipated problems to the IRB is defined as within 5 business days from becoming aware of the event.

7.4.2 Reporting to the FDA

Per CFR 312.32 (c), the investigator-sponsor of the IND must notify the Food and Drug Administration (FDA) and all participating investigators in a written IND safety report of any adverse experience. There are two types of reports to the FDA: 7-day and 15-day reports.

7-Day Reports:

The investigator-sponsor must notify the FDA and all participating investigators in a written IND safety report of any adverse experience:

- **fatal or life-threatening experience that is both**
- **suspected to be associated with use of the drug and**
- **unexpected (not in the investigator's brochure)**

The FDA will be notified as soon as possible but no later than **7 calendar days** after initial receipt of the information.

15-Day IND Reports:

Per CFR 312.32 (c), the investigator-sponsor of the IND must notify the Food and Drug Administration (FDA) and all participating investigators in a written IND safety report of any adverse experience:

- **suspected to be associated with use of the drug that is both**
- **serious and**
- **unexpected (not in the investigator's brochure)**

Each written notification shall be made as soon as possible, and no later than **15 calendar days** after the investigator-sponsor's initial receipt of the information.

Report Content

Each written notification may be submitted on FDA Form 3500A or in a narrative format and must bear prominent identification of its contents (i.e., "IND Safety Report"). For purposes of this protocol, the **MedWatch Report Form (FDA 3500A mandatory reporting), along with FDA Form 1571, and a cover letter** submitted to the appropriate FDA division, will serve as the written IND safety report. Follow-up information to a safety report should be submitted as soon as the relevant information is available.

Submit:

- MedWatch Report Form (FDA 3500A)
- FDA Form 1571
- Cover Letter

Notify the FDA via phone or fax using MedWatch 3500A (mandatory reporting form)

- [contact], option #1
- Fax: [name]

The IUSCC Protocol Development Coordinator should be contacted to assist with all FDA submissions and will be provided with a copy of all events that are reported to the FDA.

All IND submissions will be maintained in a master file in the IUSCC Clinical Trials Office.

7.4.3 Reporting to Merck

SAEs, ECIs and pregnancy reports and any other relevant safety information are to be forwarded to the Merck Global Safety [contact] within **2 working days** to Merck Global safety (Attn: Worldwide Product Safety; [contact]).

A copy of all 15 Day Reports and FDA Annual Progress Reports as required by the FDA will be submitted to Merck & Co., Inc. (Attn: Worldwide Product Safety; [contact]) at the time of submission to FDA. Investigators will cross reference this submission, according to local regulations, to the Merck Investigational Compound Number (IND) at the time of submission.

All subjects with serious adverse events must be followed up for outcome.

7.4.4 Reporting to Participating Sites

For IND safety reports originating from this study, IUSCC will distribute reports which are serious, unexpected and suspected to be associated with the study intervention (possibly, probably or definitely related) to all participating sites in the form of an Expedited Safety Report (external safety/IND report) within 15 calendar days from determination that the suspected adverse reaction qualifies for reporting. Copies of these Expedited Safety Reports will be kept on file in the IU Simon Comprehensive Cancer Center Clinical Trials Office.

When the sponsor(s) sends IND safety reports from external studies that involve the study drug(s), Multicenter Network Associate Administrator, or designee, will forward the reports to the sponsor-investigator. The sponsor-investigator, or designee, will review these reports and determine if revisions are needed to the protocol or consent. IUSCC will forward these reports to participating sites every 2 weeks.

If an adverse event or SAE requires modification of the informed consent, protocol or other study documents, participating sites will be informed by way of an amendment and during weekly teleconferences, or sooner, as deemed necessary by the Principal Investigator.

7.4.5 Reporting to the IUSCC Data Safety Monitoring Committee (DSMC)

Regardless of study sponsorship, the study team must enter all initial and follow-up SAEs, expedited, and noncompliance reports into OnCore® for review by the DSMC chair and/or

coordinator. Expedited reports may include IRB Prompt Report Forms, MedWatch, and additional SAE forms as required by the sponsor. When follow-up information is received, a follow-up report should also be created in OnCore®. This DSMC reporting requirement is in addition to any other regulatory bodies to be notified (i.e. IRB, FDA, pharmaceutical company, etc.). The DSMC chair and/or coordinator will review all SAE, expedited, and noncompliance reports monthly.

8.0 STATISTICAL METHODS

8.1 General Considerations

Statistical analysis of this study will be the responsibility of the Department of Biostatistics at Indiana University School of Medicine. Parameter estimates and relevant summary statistics will be reported for both efficacy and safety outcomes. Continuous variables will be summarized by means, medians, minima, maxima and standard deviations. Categorical variables will be summarized by frequencies and percentages. Missing data will not be imputed. Additional exploratory analysis will be conducted when appropriate. Changes from the analysis plan will not require an amendment to the protocol unless it changes a significant feature in the protocol. The statistical analysis methods are outline below.

8.2 Study Design

This is an open-label phase I/Ib clinical trial. No randomization or blinding is involved.

8.3 Analysis Populations

8.3.1 Efficacy Population

The efficacy population comprises all patients who meet the eligibility criteria, are registered onto the study, get at least one dose of study drug, and have at least one follow-up evaluation. This set will be used for efficacy analysis.

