5.6 Subject Withdrawal/Discontinuation Criteria

Subjects may withdraw consent at any time for any reason or be removed from the trial at the discretion of the investigator should any untoward effect occur. In addition, a subject may be withdrawn by the investigator or the Sponsor if enrollment into the trial is inappropriate, the trial plan is violated, or for administrative and/or other safety reasons. If a subject withdraws from the study, they will no longer receive study intervention or be followed at scheduled protocol visits. Specific details regarding discontinuation or withdrawal are provided in Section 7.1.4.1.

A subject must be discontinued from the trial for any of the following reasons:

- The subject or legal representative (such as a parent or legal guardian) withdraws consent.
- Confirmed radiographic disease progression (with the exception of pseudoprogression as described in Section 5.9)
- Any progression or recurrence of any malignancy, or any occurrence of another malignancy that requires active treatment
- Unacceptable adverse experiences as described in Section 5.2.1.7
- Intercurrent illness that prevents further administration of treatment
- Investigator's decision to withdraw the subject
- The subject has a confirmed positive serum pregnancy test
- Noncompliance with trial treatment or procedure requirements
- The subject is lost to follow-up
- Completed 24 months of uninterrupted treatment with pembrolizumab or 35 administrations of study medication, whichever is later.

Note: 24 months of study medication is calculated from the date of first dose. Subjects who stop pembrolizumab after 24 months may be eligible for up to one year of additional study treatment if they progress after stopping study treatment provided they meet the requirements detailed in Section 7.1.6.4

- Administrative reasons

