5.8 Subject Replacement Strategy

Patients who do not complete the first cycle of combination therapy during the dose finding phase will be replaced. Patients who cannot complete Cycle 1 of the expansion phase for reasons unrelated to the study drug will also be replaced.

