8.4 Sample Size, Accrual and Study Duration

A minimum of 51 and maximum of 57 subjects (3-6 per 2 dose levels in the escalation phase + 45 in three expansion cohorts) will be enrolled in this study. The primary sample size is dictated by the 3+3 design described earlier. Subjects not DLT evaluable in the finding phase will be replaced. Three expansion cohorts of up to $n = 15$ subjects each will be used to measure efficacy endpoints and is critical for the planning of the next phase of investigation. Having at least 12 patients per expansion cohort is adequate for the purposes of estimating effect sizes for larger trials for outcomes that are normally distributed or can be transformed to normality.¹⁰ Increasing to 15 per group will help account for the possibility that a few subjects may not be evaluable for efficacy. Subjects not evaluable for efficacy in the expansion phase will be replaced. A subject is not evaluable for efficacy if they do not have at least one follow-up assessment of disease status after completing 1 cycle of combination

therapy. This could be either a scan or an assessment of symptomatic deterioration. Accrual is expected to take up to 12 months.

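### The only efficacy set omits treated patients with no follow-up evaluation, which can raise ORR but never lower it, and replacement of drug-related Cycle 1 dropouts is unclear

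*Combined protocol and SAP*

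**What the plan says.** Section 8.3.1 admits eligible, registered patients who "get at least one dose of study drug, and have at least one follow-up evaluation", and adds: "This set will be used for efficacy analysis." No other efficacy set is named. Section 8.3.2 keeps every treated patient, but for safety only. Section 8.1 rules out imputation of missing data. Section 8.9 gives ORR with an exact 95% interval and PFS and OS by Kaplan-Meier, each by expansion cohort. It has no rule for patients without an assessment.

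Section 8.4 words evaluability differently. Its test, which refers to the two-drug treatment, classes patients as "not evaluable for efficacy if they do not have at least one follow-up assessment of disease status after completing 1 cycle of combination". On what counts as an assessment it says: "This could be either a scan or an assessment of symptomatic deterioration." It then states: "Subjects not evaluable for efficacy in the expansion phase will be replaced." The same section calls 12 per cohort adequate and goes to 15 because a few subjects may not be evaluable. It gives the total as "A minimum of 51 and maximum of 57 subjects".

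Section 5.8 has its own rule for the expansion phase: "Patients who cannot complete Cycle 1 of the expansion phase for reasons unrelated to the study drug will also be replaced."

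**The concern.** Membership of the efficacy set depends on something that happens after treatment starts. A treated patient with no disease assessment cannot be a confirmed responder, so leaving that patient out removes a non-responder from the denominator and nothing from the numerator. If the patient died early, a PFS event is lost as well, and OS uses the same set.

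ORR and PFS are the primary objective (Section 3.1), and Section 8.4 says the expansion cohorts are critical for planning the next phase. An upward shift would carry into that planning. Because the evaluation is undefined in 8.3.1, and 8.3.1, 8.4 and 5.8 are worded differently, two analysts following the plan could also report different denominators for the same cohort.

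**Working it through.** **1. The plan's own total.** Two dose levels of 3 to 6 patients plus 3 × 15 = 45 in expansion gives 2 × 3 + 45 = 51 and 2 × 6 + 45 = 57. Both stated figures reproduce. No response rate, early-failure rate or power figure is stated, so the counts in steps 3 and 4 are assumptions. The choice of three omitted patients follows the 8.4 allowance, 15 − 12 = 3.

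**2. Who can fall out.**
- Several provisions keep patients in. Imaging is due at discontinuation (7.1.2.5, 14.3.4). Final-visit activities are done at discontinuation or withdrawal where possible (7.1.4.1). Disease-status follow-up continues for those who stop without progression (5.6, 7.1.6.2). Section 14.3.3 sets a first scan 4 weeks from screening. Section 8.4 accepts assessed symptomatic deterioration.
- Other provisions let some out. Early deaths have no discontinuation scan. For subjects who withdraw, 5.6 says "they will no longer receive study intervention or be followed at scheduled protocol visits". The first scheduled scan is before Cycle 3 in 7.1.2.5 and at 12 weeks in 2.1. Deterioration counts in 8.4 only after one completed combination cycle, and 8.3.1 does not repeat that it counts at all.

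**3. ORR.** Let r be the responders, n the eligible treated patients and k those with no evaluation. All-treated ORR is r/n and the 8.3.1 ORR is r/(n − k). The ratio is n/(n − k), which is never below 1. Intervals are Clopper-Pearson 95%.

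| Case | All treated | 8.3.1 set | Shift (points) |
|---|---|---|---|
| Replaced, k = 1 | 5/16 = 31.3% (11.0–58.7) | 5/15 = 33.3% (11.8–61.6) | 2.1 |
| Replaced, k = 3 | 5/18 = 27.8% (9.7–53.5) | 5/15 = 33.3% (11.8–61.6) | 5.6 |
| Replaced, k = 3 | 3/18 = 16.7% (3.6–41.4) | 3/15 = 20.0% (4.3–48.1) | 3.3 |
| Not replaced, k = 1 | 5/15 = 33.3% (11.8–61.6) | 5/14 = 35.7% (12.8–64.9) | 2.4 |
| Not replaced, k = 3 | 5/15 = 33.3% (11.8–61.6) | 5/12 = 41.7% (15.2–72.3) | 8.3 |
| Not replaced, k = 3 | 3/15 = 20.0% (4.3–48.1) | 3/12 = 25.0% (5.5–57.2) | 5.0 |

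With no responders the point estimate stays at 0.

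**4. PFS.** Assume exponential PFS with true median M, and that k of 15 + k treated patients die unassessed, before any other event, and are dropped and replaced. After those deaths the remaining 15 have survival S(t) × (15 + k)/15. Setting this to one half gives an apparent median of M × log2(2(15 + k)/15).
- M = 4.0 months: 4.4 (k = 1) and 5.1 (k = 3).
- M = 2: 2.2 and 2.5. M = 8: 8.7 and 10.1.
- For k = 3 and M = 4, all three deaths must fall within 4 × log2(18/15) = 1.05 months, about 4.6 weeks.
- Patients who leave event-free at time 0 add nothing to a Kaplan-Meier curve, so if all those dropped are of this kind the median stays at 4.0. If one of three is an early death and two leave event-free, it reads 4.4.

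**5. Replacement.**
- Cycle 1 not completed for a reason unrelated to study drug, no later assessment: replaced under both 8.4 and 5.8.
- Cycle 1 not completed because of study drug, no later assessment: replaced under 8.4, not named in 5.8.
- Scanned on stopping during Cycle 1: arguably in the 8.3.1 set, yet not evaluable under 8.4 because no combination cycle was completed.

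If dose finding uses d patients, a total of 57 leaves 57 − 45 − d = 12 − d places: 6 when d = 6, 1 when d = 11, none when d = 12. Section 8.4 does not say whether replacements sit inside the limit of 15 per cohort.

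**The case against.** The strongest reply is that few patients are affected. The capture provisions in step 2 will give most early leavers, including most who stop for toxicity, some disease evaluation. On a broad reading the physical examination and ECOG status scheduled each cycle would count as a follow-up evaluation, and almost nobody would be excluded. This stands as to size. It does not remove the problem, because the broad reading is not stated and 8.4 itself plans for a few non-evaluable patients.

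A second reply is that the trial seeks early signals and plans no comparisons, and that the ORR shifts are small beside intervals about 38 to 57 points wide. That is also true. But the interval shows the imprecision, while nothing in the report would show a shift whose direction is fixed.

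A third is that the objective concerns the combination, so an all-treated set could include patients who received only run-in drug. This is a fair estimand point, and the reason for a required sensitivity set of those who started the combination.

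Two stronger readings are tempting. One is that 5.8 and 8.4 flatly contradict each other. Section 5.8 says the unrelated-reason dropouts are also replaced; it does not say that only they are, so both rules can be applied together and the defect is ambiguity. The other is that 57 leaves no room for replacements. That holds only if both dose levels take 6 patients, and it overlooks the step from 12 to 15.

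**Conclusion.** The point holds and should be fixed. Followed as written, 8.3.1 can raise ORR or leave it unchanged, and cannot lower it. Under the assumed counts the shift is 2.1 to 5.6 points with replacement and 2.4 to 8.3 points without. These figures rest on 3 or 5 responders and 1 or 3 unassessed patients per cohort, none of which the documents give.

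A reader might infer that PFS is inflated too. That follows only if the omitted patients had early events. The move from 4.0 to 5.1 months is an upper bound for three omitted patients: it needs all 3 of 18 to be early unassessed deaths, under an exponential curve. Nor do the documents support the inference that toxicity dropouts as a group disappear from the analysis.

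On replacement, the status of drug-related Cycle 1 dropouts and the way replacements count toward 15 and 57 are unclear. The total of 57 has spare places only if dose finding uses fewer than 12 patients.

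**What to change.** - In 8.3.1 and 8.9, make the main ORR and PFS set all eligible expansion patients who received at least one dose of study drug, including any who are replaced.
- Count patients with no post-baseline assessment as non-responders. Count deaths, or assessed clinical progression, before the first scan as PFS events.
- Define the follow-up evaluation in 8.3.1 in the same terms as 8.4: a scan or an assessment of symptomatic deterioration.
- Require two sensitivity analyses: the 8.4-evaluable set, and the set that started the combination.
- Reconcile 5.8 with 8.4, and report replacements per cohort with reasons. State whether replacements count within 15 per cohort. If they are additional, restate the totals in 8.4, the trial summary (1.0) and 2.1.

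The cost is wording in 8.3.1, 8.4, 8.9 and 5.8, plus 1.0 and 2.1 if the totals change, using data already collected. The downside is that ORR and PFS may look slightly less favourable, and the main set may include a few patients who received only run-in drug. The second sensitivity analysis shows the effect of the latter.

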8.3.2 Safety Population

The safety population comprises all patients who have received at least one dose of the study medication. This set will be used for safety analysis.

8.4 Sample Size, Accrual and Study Duration

A minimum of 51 and maximum of 57 subjects (3-6 per 2 dose levels in the escalation phase + 45 in three expansion cohorts) will be enrolled in this study. The primary sample size is dictated by the 3+3 design described earlier. Subjects not DLT evaluable in the finding phase will be replaced. Three expansion cohorts of up to $n = 15$ subjects each will be used to measure efficacy endpoints and is critical for the planning of the next phase of investigation. Having at least 12 patients per expansion cohort is adequate for the purposes of estimating effect sizes for larger trials for outcomes that are normally distributed or can be transformed to normality.¹⁰ Increasing to 15 per group will help account for the possibility that a few subjects may not be evaluable for efficacy. Subjects not evaluable for efficacy in the expansion phase will be replaced. A subject is not evaluable for efficacy if they do not have at least one follow-up assessment of disease status after completing 1 cycle of combination

therapy. This could be either a scan or an assessment of symptomatic deterioration. Accrual is expected to take up to 12 months.

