Once the RP2D is identified, the Dose Expansion Phase will be opened. During the Dose Expansion Phase, the study will have a run-in phase with sequential single-agents (Schema B) and then the combination phase (Schema A). The run-in phase may be waived at the investigator's discretion. The reason for the run-in phase during dose expansion is to obtain data on the immunomodulatory effects of vorinostat separately from pembrolizumab. Forty-five patients with prior treatments will be enrolled in three expansion cohorts: 15 anti-PD1 naive renal and urothelial patients, 15 anti-PD1 resistant renal and urothelial patients (defined as patients with transient clinical response or without clinical response to prior immune-checkpoint inhibition), and 15 patients with androgen-sensitive or castration-resistant prostate cancer. The prostate cohort has been added in an amendment during the Dose Expansion Phase, and therefore, will not be part of the Dose Finding Phase.

Anti-tumor activity will be assessed by radiological tumor assessments conducted at baseline, 12 weeks and every 6 weeks thereafter, using RECIST version 1.1 (see Section 14.3). RECIST 1.1 will be used for treatment decisions until first radiologic evidence of progressive disease (PD). Following the first evidence of radiologic PD, treatment decisions may be made by the adaption of RECIST 1.1, termed the immune-related response criteria (irRC) (see Section 14.6) to account for the tumor response patterns seen with pembrolizumab treatment (e.g. tumor flare).

[figure not shown]
1 Cycle = 3 weeks (21 days)

Schema B: Run-In Phase

The RP2D is the dose of pembrolizumab and vorinostat in combination chosen for further clinical development. Further experience in the Dose Expansion Cohort may result in a RP2D dose lower than the MTD.

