7.1.2.5 Tumor Imaging and Assessment of Disease

Imaging studies (CT and bone scan) will be performed at baseline, before Cycle 3, every 3 cycles thereafter and at treatment discontinuation as described in Section 7.1.4.1 below. CT modalities should be done according to standard of care for the patient's disease. Bone scans should be done at baseline and then only as clinically indicated.

Patients in Cohort C (prostate) will have two PET scans using ⁶⁸Ga-PSMA-11: once at baseline and then at 12 weeks (Cycle 4) Not all patients in Cohort C will have the additional PET scans. This determination will be made by the Principal Investigator.

Participant eligibility will be determined using local assessment (Investigator assessment) based on RECIST 1.1. In addition, images (including via other modalities) that are obtained at an unscheduled time point to determine disease progression, as well as imaging obtained for other reasons, but which demonstrate radiologic progression, should also be used to determine progression.

When the Investigator identifies radiographic progression per RECIST 1.1, efforts should be made to verify radiologic PD. Treatment should continue until PD has been verified. Regardless of whether PD is verified, if the Investigator considers the participant has progressed, but elects to implement irRC, the Investigator will assess for confirmation of progression by irRC at subsequent time points.

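### The enrolment maximum of 57 and the expansion figures of 45 and 15 leave no room for uncapped replacement, and 5.8, 8.4 and 8.3.1 define the replaceable and the analysed patient differently

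*Combined protocol and SAP*

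**What the plan says.** **Numbers.** Section 8.4 of the combined protocol and SAP gives the enrolment range as "A minimum of 51 and maximum of 57 subjects (3-6 per 2 dose levels in the escalation phase + 45 in three expansion cohorts". The trial summary (1.0) repeats 51-57. Section 2.1 states "Forty-five patients with prior treatments will be enrolled in three expansion cohorts", 15 in each, and 8.4 describes each cohort as having up to 15. Section 8.4 regards at least 12 per cohort as adequate and explains the step to 15 as cover for a few patients who turn out not to be evaluable for efficacy.

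**Replacement.** For dose finding, 8.4 says "Subjects not DLT evaluable in the finding phase will be replaced". For expansion it says "Subjects not evaluable for efficacy in the expansion phase will be replaced". Section 5.8 replaces dose-finding patients who do not complete the first combination cycle, and adds for expansion: "Patients who cannot complete Cycle 1 of the expansion phase for reasons unrelated to the study drug will also be replaced". No section caps replacements.

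**Evaluability.** Section 8.4 calls an expansion patient not evaluable if there is no disease assessment (a scan, or a judgement of symptomatic deterioration) after one completed combination cycle. The reason does not matter. Section 8.3.1 defines the efficacy set as eligible, registered patients who "get at least one dose of study drug, and have at least one follow-up evaluation"; a completed cycle is not required. In expansion, "the study will have a run-in phase with sequential single-agents (Schema B) and then the combination phase (Schema A", so a patient can be dosed and leave before any combination treatment.

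**The concern.** An enrolment maximum should be one that the plan's own rules can keep. Here the top of the range is filled entirely by the planned slots, and the replacement rules can add patients without limit. Once a cohort is full, a site with a non-evaluable patient must either leave that patient unreplaced, against 8.4, or enrol beyond the cohort figure. The plan does not say whether the aim is 12 evaluable, 15 enrolled or 15 evaluable per cohort.

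The second issue is who counts. Objective response and progression-free survival are the primary objective (3.1), are reported by cohort (8.9), and are meant to inform the next trial (8.4). With about 15 patients per cohort, whether one or two early leavers are counted shows in the response rate. The trial is open-label, so the rule should be fixed in advance.

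**Working it through.** **1. The stated range.** Two dose levels of 3 to 6 patients plus three cohorts of 15:
- minimum 3 + 3 + 45 = 51
- maximum 6 + 6 + 45 = 57

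Both reproduce with zero replacements. The whole spread of 6 comes from dose finding; expansion is 45 at both ends.

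**2. When each figure is exceeded, if 15 evaluable per cohort are required.** The first replacement in a full cohort makes 16. Once all three cohorts are full, it makes at least 46 in expansion. Neither depends on how dose finding went. The overall figure does:

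| Dose-finding patients | Base total | Spare below 57 | Replacement that makes 58 |
|---|---|---|---|
| 12 | 57 | 0 | 1st |
| 9 | 54 | 3 | 4th |
| 6 | 51 | 6 | 7th |

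**3. How likely an expansion replacement is.** The documents give no loss rate, so r is an assumption, taken as independent between patients. The chance of at least one loss among 45 is 1 − (1 − r)^45, and expected enrolment to reach 45 evaluable is 45/(1 − r).

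| Assumed r | At least one replacement | Expected expansion enrolment |
|---|---|---|
| 2% | 1 − 0.98^45 = 0.597 | 45/0.98 = 45.9 |
| 5% | 1 − 0.95^45 = 0.901 | 45/0.95 = 47.4 |
| 10% | 1 − 0.90^45 = 0.991 | 45/0.90 = 50.0 |

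**4. If 12 evaluable per cohort are enough.** Three losses per cohort (15 − 12), nine in all, fit within 45 without replacement. The chance that at least 12 of 15 are evaluable is binomial: 0.9945, 0.9444 and 0.6482 at 5%, 10% and 20% loss. For all three cohorts, the cubes are 0.984, 0.842 and 0.272.

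**5. The three rules applied to the same expansion patient.**

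| Patient | 5.8 | 8.4, read literally | 8.3.1 |
|---|---|---|---|
| Stops in Cycle 1 for drug toxicity, no later assessment | Not covered | Replaced | Left out if no follow-up evaluation |
| Stops in Cycle 1 for drug toxicity, has an evaluation | Not covered | Replaced | Analysed |
| Stops in Cycle 1 for a reason unrelated to drug, has an evaluation | Replaced | Replaced | Analysed |
| Completes Cycle 1, no later assessment | Not covered | Replaced | Left out if no follow-up evaluation |

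In the second and third rows the patient and the replacement are both analysed, so a cohort can have more than 15 in the efficacy set. A patient who leaves during the run-in and has an evaluation is in the same position under 8.4 and 8.3.1.

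**6. Effect on the response rate (illustration).** Three responders give 3/15 = 20.0%. With one or two replaced non-responders also counted, the rate is 3/16 = 18.8% or 3/17 = 17.6%.

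**The case against.** **The 12-to-15 margin may be all that is needed.** If 12 evaluable is the real aim, nine losses fit within 45. Using a margin and replacement together is cautious, not contradictory. This stands as far as it goes, but 8.4 then says that the same patients will be replaced, so the plan does not rely on the margin alone.

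**Losses may be small.** Section 8.4 accepts symptomatic deterioration as an assessment, which is a low bar. That is fair, and it is why 2% is in the range. Even there, one replacement is more likely than not.

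**The overall maximum is not breached at once.** A reader might infer that the first expansion replacement necessarily breaks 57 and the trial summary's 51-57. It does so only after 12 dose-finding patients; after 9 or 6 the total becomes 55 or 52. Nor is it useful to average over possible dose-finding paths: 2.1 says that the prostate cohort was added during expansion, so the dose-finding count was already settled when the three-cohort totals were written.

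**The efficacy set is defined.** A reader might infer that replaced patients drop out of the analysis and that the response rate is thereby biased upward. No section says so. Section 8.3.1 fixes the set, and nothing removes a replaced patient from it. Its own requirement for a follow-up evaluation does leave out those with none, whether or not anyone is replaced.

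**The replacement rules can be read together.** The expansion sentence in 5.8 is not exclusive, so 5.8 and 8.4 can be applied cumulatively, and the completed cycle in 8.4 may be meant only as timing. This softens the conflict. On the timing reading, the patient with toxicity and no assessment is still replaceable under 8.4 and not covered by 5.8.

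**An early leaver may have no scan.** Section 7.1.2.5 says "Imaging studies (CT and bone scan) will be performed at baseline, before Cycle 3, every 3 cycles thereafter and at treatment discontinuation". But 14.3.4 waives the discontinuation scan if imaging was done in the preceding 4 weeks, and 14.3.2 allows screening images up to 28 days before the first cycle. So some early leavers will have no evaluation, and the overlap between 8.4 and 8.3.1 arises only for those who have one.

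**The numerical effect is modest.** Exact 95% intervals are about 4-48% for 3/15 and 4-43% for 3/17, and 8.9 plans no comparisons. This limits the severity of the point.

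**Conclusion.** The point holds in a limited form. The arithmetic of 51 to 57 is right, but 57 enrolled, 45 in expansion and 15 per cohort are not limits that the plan's own replacement rules guarantee. That conclusion comes from the wording and needs no assumed rate. If 15 evaluable per cohort are required, the cohort and expansion figures are the ones most exposed: 60%, 90% or 99% chance of at least one expansion replacement at 2%, 5% or 10% loss, with 0.9, 2.4 or 5.0 extra expansion patients expected. These figures rest on assumed, independent losses. If 12 evaluable suffice, there need be no excess, but the plan would have to say so.

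The mismatch between 5.8, 8.4 and 8.3.1 is real but narrower than a direct contradiction. It leaves unclear which early leavers are replaced, and it allows a cohort to exceed 15 analysed. The documents do not show that replaced patients are excluded or that the response rate is biased for that reason. This should be corrected, but it does not undermine the design.

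**What to change.** 1. **Totals (1.0, 2.1, 8.4).** State that 57, 45 and 15 count evaluable subjects (for DLT in dose finding, for efficacy in expansion). Cap replacements at a in dose finding and b per expansion cohort, and give a separate enrolment maximum of 57 + a + 3b. With b = 1, 2 or 3 this is 60, 63 or 66, plus a.

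   Alternatively, if the 12-to-15 margin is meant to be the only allowance, keep 15 enrolled as the ceiling and remove expansion replacement from 5.8 and 8.4. Dose-finding replacements still need a cap, and the maximum becomes 57 + a. The price is the chance of falling below 12 evaluable shown in step 4 of the working.

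2. **Definitions (5.8, 8.3.1, 8.4).** Use one definition of an evaluable and of a replaceable expansion patient in all three sections. Say whether the completed combination cycle is a requirement or only a time point, and how patients who leave during the run-in are handled.

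3. **Analysis (8.3.1).** State that a treated patient who is replaced stays in the efficacy set. Count those who stop for toxicity, progression or death before an assessment as non-responders for objective response.

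The cost is text in five sections and no new data. The stated enrolment maximum rises, a cohort may have more than 15 analysed, and the response rate may be slightly lower.
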